## Abbreviations

ADA	Anti-Drug Antibody
AD	Atopic Dermatitis
AE	Adverse event
ALT	Alanine aminotransferase (ALT, SGPT)
PT/aPTT	Prothrombin Time/Activated Partial Thromboplastin Time
ALP	Alkaline phosphate
BMI	Body mass index
BP	Blood pressure
BSA	Body Surface Area
CBC	Complete blood counts
CI	Confidence interval
CH	Heavy chain constant region
CL	Light chain constant region
eCRF	Electronic Case report form
CRA	Clinical Research Associate
CRP	C-Reactive Protein
CTCAE	Common terminology criteria for adverse events
DLQI	Dermatology Life Quality Index
EASI	Eczema Area and Severity Index Score
EC	Ethics Committee
ECG/EKG	Electrocardiogram
ELISA	Enzyme-linked immunosorbent assay
GISS	Global Individual Signs Score
GCP	Good clinical practice
HADS	Hospital Anxiety Depression Scale
HbA1c	Hemoglobin A1c
HBsAg	Hepatitis B surface antigen
HIV	Human immunodeficiency virus
ICF	Informed Consent Form
IFN- $\gamma$	Interferon Gamma
IGA	Investigator's Global Assessment
IGRA	Interferon Gamma Release Assay
IgG	Immunoglobulin G
IL-6	Interleukin-6
IL-1 $\alpha$	Interleukin-1 $\alpha$
IL-1 $\beta$	Interleukin-1 $\beta$
IL-1 RA	Interleukin-1 receptor antagonist
IRB	Institutional review board
NRS	Numerical Rating Scale
NSAID	Non-Steroidal Anti-Inflammatory Drug
PD	PharmacodynamicspI Isoelectric Point
PK	Pharmacokinetics
POEM	Patient Oriented Eczema Measure
SAE	Serious Adverse Event
SAF	Safety analysis set
SAP	Statistical analysis plan
SAS	Statistical analysis software
SCORAD	Severity Scoring of Atopic Dermatitis
TB	Tuberculosis
UV	Ultraviolet
VAS	Visual Analogue Scale
WOCBP	Women of childbearing potential

# 1. BACKGROUND

## 1.1 OVERVIEW

XBiotech USA, Inc. has developed a True Human recombinant IgG1 monoclonal antibody, bermekimab, that binds the cytokine interleukin-1alpha (IL-1 $\alpha$ ) with high affinity and is an effective blocker of IL-1 $\alpha$  biological activity. IL-1 $\alpha$  is a key mediator of sterile inflammatory responses and has been implicated in the pathology of advanced cancer, cardiovascular disease, and rheumatologic disease. Clinical evidence generated to date suggests that targeting IL-1 $\alpha$  may be an effective means of undermining the inflammatory process that drives a wide array of diseases, including dermatologic conditions.

The active ingredient in the drug product bermekimab is MABp1, a recombinant human IgG1 monoclonal antibody specific for human interleukin-1 $\alpha$  (IL-1 $\alpha$ ). The entire MABp1 heavy and light chain sequences are identical to those found in naturally-occurring human IgG1 $\kappa$ , with the light and heavy chain variable regions being identical to those originally expressed by a peripheral blood B lymphocyte that was obtained from a healthy individual. No *in vitro* affinity maturation or modifications have been made to improve its natural binding affinity (211 +/- 31 pM). We believe that a true human antibody should be effectively non-immunogenic in humans and thus exhibit optimal activity and pharmacokinetics.

XBiotech has conducted 13 clinical studies to date using the bermekimab antibody. These studies have been conducted in a wide range of therapeutic areas, from cancer to healthy volunteers, and have included several different dose levels and dosing schedules. Both intravenous and subcutaneous formulations have been explored for safety and evidence of efficacy. Five Phase II studies sponsored by XBiotech have been completed in dermatologic indications (psoriasis [NCT01384630], acne vulgaris [NCT01474798], pyoderma gangrenosum [NCT01965613], atopic dermatitis [NCT03496974], and hidradenitis suppurativa [NCT03512275]), as well as one investigator sponsored study in Hidradenitis Suppurativai,ii,iii.

Subjects with moderate to severe psoriasis experienced a rapid reduction in their psoriasis area and severity index (PASI), and subjects with acne vulgaris experienced reductions of inflammatory lesion counts, as well as reduced hospital anxiety and depression scores (HADS). Similarly, when MABp1 was used in patients with pyoderma gangrenosum, there was a marked improvement in lesions over a short period of time. In the two most recent studies for hidradenitis suppurativa and atopic dermatitis, statistically significant improvement was seen for nearly every efficacy endpoint by the end of the study.

Results from atopic dermatitis study showed that bermekimab appeared to be safe, well tolerated, and active at reducing the severity of atopic dermatitis, including reducing itch and pain. This study was a phase II, open label, dose escalation study of bermekimab in subjects with moderate to severe atopic dermatitis. Thirty-eight patients across 9 clinical sites in two treatment groups received one of two subcutaneous (SC) doses: a low (200 mg, n=10) or high (400 mg, n=28) dose of bermekimab once weekly for either a 4 or 8-week treatment regimen, respectively. Safety was assessed by pre- and post-treatment measurements of vital signs, clinical laboratory assessments (blood chemistry, urinalysis, hematology), allergic reaction monitoring, and adverse event monitoring. Efficacy was assessed by change in EASI, IGA, NRS, SCORAD, POEM, DLQI, and GISS from baseline to visit 9. The primary measure of efficacy was the EASI. In the study, 39% of high dose patients achieved 75% improvement in EASI score (EASI-75) after 4 weeks of therapy and 75% of patients achieved EASI-75 at week 8. Of note, participants were not allowed to use concomitant topical corticosteroids during the study and thus these improvements were most likely due to the study drug alone.

While clinically and statistically significant improvement was seen for all clinical endpoints in the high dose group, also notable was the speed, magnitude, and trajectory of responses seen. In the high dose group, for example, after only four weeks of treatment, 61% of patients achieved a 4-point improvement in the Pruritus Numerical Rating Scale (NRS) for overall itch; and 75% of patients achieved a 4-point improvement by week 8. For the Pruritus Numerical Rating Scale (NRS) – worst moment itch after only four weeks of treatment, 63% of patients achieved a 4-point improvement and 78% of patients achieved a 4-point improvement by week 8. Furthermore, 80% of patients achieved a 4-point improvement in the Numerical Rating Scale (NRS) for pain by week 8.

Overall, bermekimab appeared safe, well tolerated, and showed significant therapeutic activity in most subjects. In all of these trials, there were few adverse events, most of which were grade 1 (mild).

## **1.2 RATIONALE**

Atopic dermatitis (AD), is an inflammatory skin disease affecting 1-20% of the adult population. Chronic eczema in AD and associated pruritus can be a significant cause of morbidity and can impact quality of life. Disease pathogenesis is complex but ultimately converges on a pathological inflammatory process that disrupts the protective barrier function of the skin.

IL-1 $\alpha$  plays a key role in the pathophysiology of a wide range of inflammatory skin disordersv. Keratinocytes are a major reservoir of IL-1 $\alpha$  and may be a key source of inflammatory stimulus in AD. IL-1 $\alpha$  is present on leukocytes, where its role in leukocyte trafficking and infiltration may represent an essential step in the chronic inflammation of AD. IL-1 $\alpha$  is a key inducer of matrix metalloproteinases activity which could be directly involved in the epithelial barrier breakdown in ADvi. Further, in a study by Archer et al, IL-1 $\alpha$ , rather than IL-1 $\beta$ , was not only a fundamental component for inducing chronic skin inflammation, but the primary driving forcevii. The study included mice with epidermal birth defects and showed that keratinocytes, which constitute approximately 90% of skin cells, secrete aberrant stores of intracellular IL-1 $\alpha$  in response to skin injury (e.g. scratching), leading to chronic skin inflammation. Atopic Dermatitis is strongly associated with epidermal barrier defects, most commonly caused by mutated copies of the filaggrin geneviii. Filaggrin deficiencies are associated with changes in the composition of bacteria living on the skin, whereby bacteria can colonize and infect the skin with greater success thereby exacerbating aberrant IL-1 $\alpha$  secretionix. Neutralizing IL-1 $\alpha$  activity resolved chronic skin inflammation in this study and strongly supported IL-1 $\alpha$  as a key target for treating atopic dermatitis, along with other inflammatory skin diseases.

[figure not shown]
Endogenous anti-IL-1 $\alpha$  antibodies are present in 5% to 28% of the general populationx,xi,xii,xiii. No negative correlations with disease have been noted for these individuals. To the contrary, the presence of natural anti-IL-1 $\alpha$  antibodies has been associated with favorable outcomes, both with respect to rheumatoid arthritis and ischemic heart disease. Animal studies also indicate that IL-1 $\alpha$  loss or antagonism does not result in harm. Moreover, the well-tolerated use of other approved biological agents that employ alternative strategies to block IL-1 activity suggest that MABp1's targeting of IL-1 $\alpha$  represents a safe treatment approach.

In previous dermatology studies bermekimab was well tolerated and showed impressive therapeutic activity. The safety data from XBiotech's open label studies: PT044 atopic dermatitis and PT045 hidradenitis suppurativa established good levels of safety and tolerability for 400mg bermekimab (2mL of 200mg/mL) subcutaneous injections and in both studies no safety signals were identified and no study stopping rules were met.

## 2. INVESTIGATIONAL PRODUCT

### 2.1 ACTIVE INGREDIENT, PHARMACOLOGIC CLASS, STRUCTURE

**Figure 2: Bermekimab Antibody**

The bermekimab primary glycoform has a molecular weight of 148.1 kilodaltons. Like all IgG1 molecules, the heavy chains are joined at their hinge regions through two disulfide linkages, and each heavy chain is joined to one light chain through one disulfide linkage between their CH1 and CL domains respectively.

The main isoform has a pI of about 9.2 and comprises about 70-80% of the total isoform population in all lots that have been manufactured to date, as determined by capillary isoelectric focusing. The heavy chain CH2 domains are glycosylated primarily with the oligosaccharide structure shown in Figure 2, as determined by mass spectroscopy of the cleaved glycans. The glycosylated residue (Asn-302 as numbered from the N-terminus of bermekimab) has been determined by peptide mapping to be in the same highly conserved N-linked glycosylation site as found in endogenous IgG1 (Asn-297 according to the generic numbering system). Similarly, the primary glycan, commonly referred to as G0F, is the same as that found on about 22% of endogenous human IgG moleculesxiv.

The entire bermekimab heavy and light chain sequences are identical to those found in naturally-occurring human IgG1 $\kappa$ , with the light and heavy chain variable regions being identical to those originally expressed by a peripheral blood B lymphocyte that was obtained from a healthy individual.

Endogenous anti-IL-1 $\alpha$  antibody has been reported in 5% to 28% of healthy serum or plasma samplesx,xi and cord bloodxv. The anti-IL-1 $\alpha$  antibodies measured in human plasma are IgG, in particular IgG1, IgG2, and IgG4 subclasses. Relatively equal prevalence for these antibody are seen in male and female plasmaxvi. Binding affinities reported for endogenous anti-IL-1 $\alpha$  antibodies, ranging from 4 to 16 pM, are comparable to that for bermekimab, the specification for which is 22 to 260 pM.

It is important to point out that affinity maturation had already taken place in the human host, and therefore no *in vitro* affinity maturation was required to increase the natural binding affinity of MABp1. Also important is the fact that, unlike most other therapeutic IgG products, for which the Fc regions are derived from a rare human allele, XBiotech's product includes a heavy chain in which the constant (CH) region represents an allele found in approximately 70% of the human population. These two features should make for a drug product with reduced potential for immunogenicity.

## **2.2 DRUG PRODUCT (BERMEKIMAB 200 MG/ML) DESCRIPTION**

XBiotech's dosage form is a sterile liquid formulation of 200 mg/mL bermekimab in a stabilizing isotonic subcutaneous formulation buffer at pH 6.2-6.5 containing non-active ingredients of low concentrations of sodium phosphate, citric acid and trehalose. The drug product is packaged in pre-filled syringes. Drug product in syringes is stored at 2-8°C and is recommended to be protected from light.

## **2.3 STORAGE**

The recommended storage condition is at 2-8°C.

## **2.4 STABILITY**

The drug product is formulated in a buffer in which most of the tonicity comes from trehalose rather than salt. Trehalose is an effective stabilizer against oxidation, aggregation, and thermal or mechanical stress. Citrate was selected as the buffering agent due to its antioxidant properties.

Extensive stability data indicates that the drug product is very stable, even under thermally and mechanically stressed conditions. Short excursions to room temperature have been shown to have no negative effect on the product. However, the study treatment products are not to be frozen at any time. The drug product is labeled with a 12-month retest date. Every lot is also subjected to ongoing stability analysis per ICH guidelines.

## **2.5 DESIGNATED INDIVIDUAL FOR DRUG ADMINISTRATION**

To ensure that no unintentional unblinding occurs during study drug administration, a qualified individual will be designated at each study site to perform all preparation and injection of the investigational product. The designated injector should have no other contact with the participant during the study, should not discuss the participant's treatment with the participant, participant's caregiver, or other site personnel at any time, and will not be permitted to review the participant's medical records, questionnaires, or the

electronic CRF prior to each injection. The designated injector should be documented in the source documents at each visit.

## 2.6 METHOD OF ADMINISTRATION

Each injection should be administered at least one inch from previous injection sites.

### Instructions For Subcutaneous Injection

**\* At least 45 minutes prior to injection, remove the pre-filled syringe from refrigeration.**

*Lay the syringe on a flat surface and let it naturally warm to room temperature before injection. It may also be warmed by holding in hand. Do not heat the syringe.*

### Materials

Bermekimab pre-filled syringe for injection, warmed to room temperature

Sterile alcohol wipes

Band-aids, along with 2x2 gauze bandages and paper tape

[figure not shown]
Latex-free gloves

### Injection Site

**Abdomen, at least 2 inches away from the belly button (Figure 3)**

*(Note: avoid areas where the skin is burned, scarred, hardened, inflamed, swollen or damaged)*

**Figure 3**

### Injection

- Put on gloves
- Wipe injection site clean with alcohol pads

- Raise a fold of skin between the thumb and forefinger and insert needle as illustrated (Figure 4).
- Inject drug as rapidly as is comfortable for the patients.
- Withdraw needle. Place band-aid over injection site if desired (*Note: If bleeding occurs, hold pressure on the injection site for 90 seconds or until bleeding stops, and then apply gauze bandage secured by tape*).

**Figure 4**

## **2.7 AGENT ORDERING**

The Responsible Investigational Pharmacy will order study drug from XBiotech’s contract drug distributor as needed.

## **2.8 POTENTIAL DRUG INTERACTIONS**

There are no known drug interactions reported with bermekimab.

## **2.9 CONCOMITANT THERAPY**

### **2.9.1 Antihistamine/NSAID Use**

Concomitant medications such as antihistamines and/or NSAIDs (ibuprofen is recommended) are allowed based on the Investigator’s judgement, in order to prevent or treat injection site reaction or discomfort. This information must be captured in eCRF.

### **2.9.2 Required Treatment**

All patients are required to apply moisturizers at least twice daily for at least 7 days before visit 1 (day 0) and to continue the treatment throughout the study (up to 36 weeks where applicable). All types of moisturizers are permitted, but patients may not initiate treatment with prescription moisturizers or moisturizers containing additives during the screening period or during the study. Patients may continue

using stable doses (for at least 7 days prior to screening visit) of such moisturizers if initiated before the screening visit. All moisturizer use must be captured in eCRF.

### **2.9.3 Permitted Medications and Procedures**

Use of concomitant medications is permitted if not listed in section 2.9 Prohibited Medications and Procedures. Permitted concomitant medications includes basic skin care (cleansing and bathing, including bleach baths), moisturizers (required as background treatment), topical anesthetics, antihistamines, and topical and systemic anti-infective medications for any duration. In addition, medications used to treat chronic disease such as diabetes, hypertension, and asthma are permitted.

Any questions regarding treatment with concomitant medication during the study, should be directed to the medical monitor.

## **2.10 PROHIBITED MEDICATIONS AND PROCEDURES**

Treatment with the following concomitant medications is *prohibited* during the entire duration of the study:

- Topical tacrolimus and pimecrolimus
- Treatment with a live (attenuated) vaccine
- Treatment with other investigational drugs (besides Bermekimab)
- Treatment with topical corticosteroids or topical calcineurin inhibitors; such agents may be administered during the study only if required for atopic dermatitis rescue. If topical corticosteroids and/or topical calcineurin inhibitors are used during the study, study treatment may continue as planned.
- Treatment with systemic corticosteroids or nonsteroidal systemic immunosuppressive drugs (e.g., cyclosporine, methotrexate, mycophenolate-mofetil, azathioprine, etc.), except if required for atopic dermatitis rescue, or if critically medically needed to treat concurrent medical conditions (e.g., asthma).
  - The use of systemic corticosteroids for indications other than AD should be limited to situations for which, in the opinion of the treating physician, there are no adequate alternatives. They should be used on a short-term basis, preferably for  $\leq 2$  weeks. Longer-term use of corticosteroids should be discussed with the medical monitor or designee and may require discontinuation of study drug. Inhaled, otic, ocular, nasal or other routes of mucosal delivery of corticosteroids are allowed throughout the study.
- Leukotriene inhibitors

- Allergen immunotherapy
- Systemic treatment for AD with an immunosuppressive/immunomodulating substance (including, but not limited to, cyclosporine, mycophenolate-mofetil, IFN- $\gamma$ , azathioprine, methotrexate, or biologics)

Study drug will be discontinued if any of the following are used through week 16:

- Treatment with a live (attenuated) vaccine
- Treatment with investigational drugs other than bermekimab.
- Treatment with systemic corticosteroids or nonsteroidal systemic immunosuppressive drugs (e.g., cyclosporine, methotrexate, mycophenolate-mofetil, azathioprine, etc.)

The following concomitant procedures are prohibited during study participation:

- Surgical procedures
- Concomitant ultraviolet (UV) procedures (phototherapy [NBUVB, UVB, UVA1, or PUVA])
- Tanning in a bed/booth
- Patients are not allowed more than 2 bleach baths per week during study participation

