## **2.11 RESCUE TREATMENT**

Rescue treatment for AD may be provided to patients if medically necessary (ie, to control intolerable AD symptoms) at the discretion of the investigator. Topical calcineurin inhibitors may be used for rescue treatment, but should only be used for problem areas (e.g. face, neck, intertriginous and genital areas, etc). If possible, investigators should attempt to limit the first line of rescue treatment to topical medications. However, if the patient does not respond adequately to topical medications after at least 7 days, systemic medications may be used.

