The mechanism behind infusion or injection site reactions is not well understood. In some cases, it may involve a reaction against the antibody products themselves, particularly where the primary sequence of the antibody has been modified *in vitro* or is derived from non-human system or, against some minor residual component from the manufacturing process (i.e. host cell proteins). Bermekimab is derived from and has undergone immunological selection in humans, thus anti-bermekimab responses are highly unlikely. To date, there has been a very low incidence of injection site or infusion reactions observed (27 patients out of 911 total; 3.0%). In order to mitigate this class-specific risk, close monitoring is required during the bermekimab infusion/ injection and for at least 30 minutes after the end of the infusion/ injection for the first 3 doses. Availability of resuscitation equipment must be ensured although this has never been used for any patient in any of our studies. Pre-medication with antihistamines, NSAIDs or corticosteroids is not required but allowed at PI's discretion.

An expanded discussion of potential risks and monitoring with bermekimab therapy is located in Section 4.6 of the Investigator's Brochure.

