### **5.3.3. Data Handling**

Participants who discontinued treatment prior to Week 16 will be considered EASI-75 non-responder at Week 16. In addition, participants with missing EASI evaluation at Week 16 will be considered as non-responders at Week 16.

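### Protocol 2.10 is inconsistent on whether systemic corticosteroid or immunosuppressant use before Week 16 stops study drug, and under the SAP the site's reading can decide whether a patient who meets EASI-75 counts as a responder

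*Protocol*

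**What the plan says.** Protocol 2.10 contains two lists.

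The first covers the whole study. It prohibits systemic corticosteroids and nonsteroidal immunosuppressants "except if required for atopic dermatitis rescue, or if critically medically needed to treat concurrent medical conditions", with asthma as the example. On corticosteroids for reasons other than atopic dermatitis (AD) it adds: "They should be used on a short-term basis, preferably for" two weeks or less, and "Longer-term use of corticosteroids should be discussed with the medical monitor or designee and may require discontinuation of study drug". A separate bullet bars systemic immunosuppressive treatment of AD and carries no rescue exception.

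The second list opens "Study drug will be discontinued if any of the following are used through week 16". One of its entries is "Treatment with systemic corticosteroids or nonsteroidal systemic immunosuppressive drugs", with no exception for indication, duration or rescue.

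Other protocol sections bear on the same question:
- 2.11: "if the patient does not respond adequately to topical medications after at least 7 days, systemic medications may be used". Neither study drug nor Week 16 is mentioned.
- 5.3: prohibited medication is not among the reasons for which therapy must stop.
- 9.7: premedication with antihistamines, "NSAIDs or corticosteroids is not required but allowed at" the investigator's discretion. No route is given.
- 10.5.3.1: a patient is a non-responder once rescue begins, and also if he or she leaves the study before Week 16. Stopping study drug is not itself named.

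The SAP differs. Section 5.3.3 says: "Participants who discontinued treatment prior to Week 16 will be considered EASI-75 non-responder at Week 16", and 5.2.2 agrees. The primary estimand in 5.3.2 has treatment discontinuation as its only intercurrent event and includes rescue in the treatment regimen.

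**The concern.** Take a patient given a short systemic corticosteroid course for asthma at Week 8. The second list in 2.10 says study drug *will* stop. The first allows the course and says that longer use only *may* lead to stopping, so a short course by implication does not. The protocol does not say which list prevails.

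The site's choice then enters the primary endpoint. If the patient meets EASI-75 at Week 16, the SAP records a responder where drug continued and a non-responder where it stopped, for the same skin and the same medication.

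Systemic rescue reaches the same result by another route. The protocol's rescue rule would give one answer whatever the site did. The SAP's primary estimand does not carry that rule, so stopping drug becomes the deciding event.

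**Working it through.** **1. Plan's own figure.** Inputs from protocol 10.1: 60% against 20%, two-sided alpha 0.05, Pearson chi-square, 80% power.

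n = [1.960 × √(2 × 0.4 × 0.6) + 0.842 × √(0.6 × 0.4 + 0.2 × 0.8)]² / 0.4² = (1.358 + 0.532)² / 0.16 = 22.3, so 23 per arm and 69 in total. This reproduces the plan. Power is 81.2% at 23 per arm and 90.6% at the planned 30. The sample size is not in dispute.

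**2. Week 16 status of a patient who took a systemic agent before Week 16 and stayed in the study.**

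| Use | Meets EASI-75 at Week 16? | Study drug | SAP 5.2.2, 5.3.2, 5.3.3 | Protocol 10.5.3.1 |
|---|---|---|---|---|
| AD rescue | Yes | continued | responder | non-responder |
| AD rescue | Yes | stopped | non-responder | non-responder |
| Other indication | Yes | continued | responder | responder |
| Other indication | Yes | stopped | non-responder | responder |
| Either | No | either | non-responder | non-responder |

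In the SAP column, status turns on the stop decision whenever EASI-75 is met. In the protocol column it never does. Patients below EASI-75 are non-responders throughout.

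**3. One patient.** 1/30 = 3.3 points. As an illustration with 6/30 responders on placebo (20%), 14/30 on active gives p = 0.029 and 13/30 gives p = 0.052 (unstratified Pearson; the planned test is the stratified CMH).

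**4. Range.** The documents give no rate of systemic use. Assume a share u of 0-10% in an arm, with users responding like the rest of the arm at rate r. The gap between every site continuing and every site stopping is u × r:
- weekly bermekimab: 10% × 60% = 6 points, so 0-6;
- placebo: 10% × 20% = 2 points, so 0-2.

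**5. Effect on the comparison at u = 10%, 30 per arm.**

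| Arms in which responders are reclassified | Rates | Difference | Power |
|---|---|---|---|
| none | 60% v 20% | 40 points | 90.6% |
| both | 54% v 18% | 36 points | 84.6% |
| active only | 54% v 20% | 34 points | 79.4% |
| placebo only | 60% v 18% | 42 points | 93.6% |

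The difference can move either way, depending on which arm is affected.

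**The case against.** The strongest reply is that the two lists do different jobs. One says what may be given; the other says what then happens to study drug through Week 16. A site can give systemic rescue and also stop drug. The sentence about longer corticosteroid use can be read as applying after Week 16, with the specific rule governing before it. For topical agents 2.10 says that study treatment may continue, and it says nothing of the kind for systemic agents.

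Much of this stands. A reader might infer that these sections cannot all be followed, and for systemic rescue that goes too far, because permission to rescue and a duty to stop are compatible. The time-limited reading of the short-course text is possible, but 2.10 does not state it: the permissive list covers the entire study, no order of precedence is given, and 5.3 is silent. Short courses for non-AD conditions before Week 16 are therefore the firmest conflict.

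A reader might also infer that 9.7 permits systemic corticosteroid premedication and so confounds a monotherapy endpoint. The text does not support that. It gives no route and is written for the whole programme, infusions included. Section 2.9.1, on preventing injection-site reactions in this trial, gives antihistamines and NSAIDs as its examples. The conflict exists only if the premedication is systemic.

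There are also safeguards. Section 2.9.3 sends concomitant-medication questions to the medical monitor. SAP Supplementary Analysis 2 uses observed EASI-75 regardless of discontinuation. SAP 4.5 and 4.6 summarise excluded therapy as deviations and list treatments that could improve AD. These make the problem visible but leave the primary analysis as it is. The per-protocol set does not exclude prohibited medication.

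**Conclusion.** The concern holds in a limited form. Section 2.10 is inconsistent for short non-AD systemic courses before Week 16, and 2.11 and 5.3 leave the consequence of systemic rescue for study drug unstated. Under the SAP, the site's decision to stop or continue settles primary-endpoint status for a systemic user who meets EASI-75 at Week 16. For rescued patients this arises only because the SAP departs from protocol 10.5.3.1.

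The size is 3.3 points per such patient. It is 0-6 points on weekly bermekimab and 0-2 on placebo if 0-10% of patients use these agents and respond at the planned rates. Both conditions are assumptions. Patients who need systemic rescue may respond less often than others, which would make the shift smaller.

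Two stronger readings are not supported. One is that identical users at different sites always receive opposite endpoint values; only those who meet EASI-75 do. The other is that 10% use means a 10-point shift; that would require every user to be a responder. The direction of any bias cannot be derived from the documents.

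**What to change.** 1. **Protocol.** Reconcile both lists in 2.10 with 2.11, 5.3 and 9.7 in one statement, including the route of any corticosteroid premedication. Which clinical rule applies is for the sponsor's clinicians.
2. **SAP, rescue.** Align 5.2.2, 5.3.2 and 5.3.3 with protocol 10.5.3.1, so that rescue before Week 16 is scored as non-response from its start whether or not drug was stopped.
3. **SAP, other systemic use.** State one scoring rule for non-rescue systemic corticosteroid or immunosuppressant use before Week 16, based on recorded medication dates and not on whether the site stopped drug. Without it, the firmest conflict would still depend on the site.

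The SAP changes should be settled before the Week 16 database lock, when some sponsor staff are unblinded.

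The cost is a protocol clarification or amendment and a few SAP sentences. No new data are needed: concomitant medication is already recorded, and SAP 4.6 already needs its dates. The downside is that response rates may be slightly lower. The protocol's rescue rule is not limited to systemic agents, so item 2 also affects patients rescued with topical treatment; the documents give no rate for that either.
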